10.10.4. Substudy B Design

10.10.4.1. Overall Design

This is a randomized, single-blinded (sponsor-unblinded) substudy to evaluate the safety and immunogenicity of the vaccination schedules detailed below. The design of Substudy B is summarized in Section 1.2.2.

Participants 65 to 85 years of age will be randomized to one of the following vaccination schedules at Visit 201 (Vaccination 1) and will be blinded to which 1-visit or 2-visit vaccination schedules they will receive:

2-Visit Schedules

- 2 Doses of qIRV encoding 2 A strains and 2 B strains at a dose level of administered 21 days apart.
- 2 Doses of licensed QIV, administered 21 days apart (as a control group).
- A dose of licensed QIV following by a dose of bIRV encoding 2 A strains at a dose level of either CCl administered 21 days apart.

1-Visit Schedules

- A dose of licensed QIV administered concurrently in the opposite arm with bIRV encoding 2 A strains at a dose level of either CC.
- A dose of bIRV encoding 2 A strains at a dose level of concurrently in the opposite arm with bIRV encoding 2 B strains at a dose level of concurrently in the opposite arm with bIRV encoding 2 B strains at a dose level of concurrently in the opposite arm with bIRV encoding 2 B strains at a dose level of concurrently in the opposite arm with bIRV encoding 2 B strains at a dose level of concurrently in the opposite arm with bIRV encoding 2 B strains at a dose level of concurrently in the opposite arm with bIRV encoding 2 B strains at a dose level of concurrently in the opposite arm with bIRV encoding 2 B strains at a dose level of concurrently in the opposite arm with bIRV encoding 2 B strains at a dose level of concurrently in the opposite arm with bIRV encoding 2 B strains at a dose level of concurrently in the opposite arm with bIRV encoding 2 B strains at a dose level of concurrently in the opposite arm with bIRV encoding 2 B strains at a dose level of concurrently in the opposite arm with bIRV encoding 2 B strains at a dose level of concurrently in the opposite arm with bIRV encoding 2 B strains at a dose level of concurrently encoding 2 B strains at a dose level of concurrently encoding 2 B strains at a dose level of concurrently encoding 2 B strains at a dose level of concurrently encoding 2 B strains at a dose level of concurrently encoding 2 B strains at a dose level of concurrently encoding 2 B strains at a dose level of concurrently encoding 2 B strains at a dose level of concurrently encoding 2 B strains at a dose level of concurrently encoding 2 B strains at a dose level of concurrently encoding 2 B strains at a dose level of concurrently encoding 2 B strains at a dose level of concurrently encoding 2 B strains at a dose level of concurrently encoding 2 B strains at a dose level of concurrently encoding 2 B strains at a dose level of concurrently encoding 2 B strains at a dose level of concurrently encoding 2 B strains at a dose level of concurrently encoding 2 B strains at a dose level of concurren
- A dose of qIRV encoding 2 A strains and 2 B strains at the following dose level combinations:

• A dose of licensed QIV (as a control group).

It is anticipated that the following strains will be used in the bIRV, but the final strain selection will be detailed in the IP manual:

It is anticipated that the following strains will be used in the qIRV, but the final strain selection will be detailed in the IP manual:

The strains used in qIRV may vary depending on the time of enrollment relative to the annual influenza season.

Substudy B enrollment of participants 65 to 85 years of age will be separated into an initial and expanded enrollment. Depending on the availability of study intervention and operational prioritization, groups of participants 65 to 85 years of age in Substudy B may not all be randomized concurrently; however, a minimum of 2 groups will be open for randomization at any one time. Participants 18 to 64 years of age will only be included in the study during expanded enrollment: 240 participants 18 to 64 years of age will be randomized 1:1 to receive either a single dose of QIRV (encoding 2 A strains and 2 B strains at a dose level of QIRV (encoding 2 A strains and 2 B strains at a dose level of QIRV (encoding 2 A strains and 2 B strains at a dose level of QIRV (encoding 2 A strains and 2 B strains at a dose level of QIRV (encoding 2 A strains and 2 B strains at a dose level of QIRV (encoding 2 A strains and 2 B strains at a dose level of QIRV (encoding 2 A strains and 2 B strains at a dose level of QIRV (encoding 2 A strains and 2 B strains at a dose level of QIRV (encoding 2 A strains and 2 B strains at a dose level of QIRV (encoding 2 A strains and 2 B strains at a dose level of QIRV (encoding 2 A strains and 2 B strains at a dose level of QIRV (encoding 2 A strains and 2 B strains at a dose level of QIRV (encoding 2 A strains and 2 B strains at a dose level of QIRV (encoding 2 A strains at a dose level of QIRV (encoding 2 A strains at a dose level of QIRV (encoding 2 A strains at a dose level of QIRV (encoding 2 A strains at a dose level of QIRV (encoding 2 A strains at a dose level of QIRV (encoding 2 A strains at a dose level of QIRV (encoding 2 A strains at a dose level of QIRV (encoding 2 A strains at a dose level of QIRV (encoding 2 A strains at a dose level of QIRV (encoding 2 A strains at a dose level of QIRV (encoding 2 A strains at a dose level of QIRV (encoding 2 A strains at a dose level of QIRV (encoding 2 A strains at a dose level of QIRV (encoding 2 A strains at a dose level of QIRV (encoding 2 A s

During initial enrollment (participants 65 to 85 years of age):

- Each group (vaccine formulation/dose level, or control) will comprise 15 participants. Hence, Substudy B initial enrollment will comprise approximately 90 participants.
- Enrollment will be controlled for the first group in which the total dose of modRNA vaccine administered at a single vaccination is **CCI**, and also for the first group in which the total dose is **CCI** as follows:
 - No more than 5 participants can be vaccinated on the first day.
 - Vaccination of the remaining participants will commence no sooner than 24 hours after the fifth participant received his or her vaccination.
- Safety and immunogenicity data accumulated at least 1 week following the last vaccination in each group will be reviewed by the sponsor's IRC and, if deemed acceptable, an additional 120 participants 65 to 85 years of age will be enrolled in that group (expanded enrollment).
- If a group is not selected for enrollment expansion or, based on review of immunogenicity data at the 4-week time point, at the sponsor's discretion, subsequent collection of blood samples from participants in that group may be halted and/or not analyzed.

As detailed above, Substudy B expanded enrollment will comprise group(s) of 120 participants following the vaccination schedule(s) as selected by the sponsor's IRC from initial enrollment. Additionally,

• 240 participants 18 to 64 years of age will be randomized 1:1 to receive either a single dose of CCI qIRV (encoding 2 A strains and 2 B strains at a dose level of CCI qIRV (encoding 2 A strains and 2 B strains at a dose level of CCI.).

- Expanded-enrollment groups may also be included that comprise only the first dose from 2-visit—schedule initial enrollment groups, eg, 1 dose of qIRV at a dose level of ...
- At the discretion of the sponsor's IRC, a control group of 120 participants may be enrolled during expanded enrollment who will receive a dose of licensed QIV followed by placebo, administered 21 days apart.

Therefore, Substudy B expanded enrollment will consist of approximately 120 to 1725 participants, depending on the number of groups selected to progress to expanded enrollment.

Stopping rules will apply throughout initial and expanded enrollment as detailed in Section 10.10.8.6.

All participants will be asked to complete a reactogenicity e-diary for 7 days following each vaccination. Blood samples of approximately 50 mL will be collected for immunogenicity assessments prior to Vaccination 1, prior to Vaccination 2 (if applicable), and at 1, 4, and 8 weeks after the participant's last vaccination.

The total duration of the study for each participant will be up to approximately 8 months.

All participants will be asked to provide an additional blood sample of approximately 2.5 mL at time points specified in Section 10.10.1 for assessment of troponin I.

All participants enrolled prior to expanded enrollment will be asked to provide an additional blood sample of 50 mL at time points specified in Section 10.10.1 for assessment of cell-mediated immunogenicity.

During expanded enrollment, all or a subset of participants will be asked to provide an additional optional blood sample of 50 mL at time points specified in Section 10.10.1 for assessment of cell-mediated immunogenicity. The number of participants asked to provide these samples will be determined by Pfizer, contingent on operational considerations.

10.10.4.2. Scientific Rationale for Study Design

See Section 2.1.

10.10.4.3. Justification for Dose

See Section 4.3.

10.10.4.4. End of Study Definition

See Section 4.4.

10.10.5. Substudy B Population

10.10.5.1. Substudy B Inclusion Criteria

Participants are eligible to be included in Substudy B only if all of the following criteria apply:

		Substudy B
Ag	e and Sex:	
1.	During enrollment of Groups 1 to 12 (Table 6): male or female participants 65 to 85 years of age at Visit 201 (Day 1) or,	X
	During enrollment of Groups 13 and 14 (Table 6): male or female participants 18 to 64 years of age at Visit 201 (Day 1).	
	• Refer to Appendix 4 for reproductive criteria for male (Section 10.4.1) and female (Section 10.4.2) participants.	
Ty	pe of Participant and Disease Characteristics:	
2.	Participants who are willing and able to comply with all scheduled visits, vaccination plan, laboratory tests, lifestyle considerations, and other study procedures.	X
3.	Healthy participants who are determined by medical history, physical examination (if required), and clinical judgment of the investigator to be eligible for inclusion in the study.	X
	Note: With the exception of heart disease, which is exclusionary (see exclusion criterion 16), healthy participants with preexisting stable disease, defined as disease not requiring significant change in therapy or hospitalization for worsening disease during the 6 weeks before enrollment, can be included. Specific criteria for participants with known stable infection with HIV, HCV, or HBV can be found in Section 10.11.	
4.	For participants 65 to 85 years of age at the time of enrollment, receipt of licensed influenza vaccination for the 2021-2022 northern hemisphere season >4 months (120 days) before study intervention administration.	X
Inf	ormed Consent:	
5.	Capable of giving signed informed consent as described in Appendix 1, which includes compliance with the requirements and restrictions listed in the ICD and in this protocol.	X

10.10.5.2. Substudy B Exclusion Criteria

Participants are excluded from Substudy B if any of the following criteria apply:

	Substudy B
Medical Conditions:	
1. Other medical or psychiatric condition including recent (within the past year) or active suicidal ideation/behavior or laboratory abnormality that may increase the risk of study participation or, in the investigator's judgment, make the participant inappropriate for the study.	X
2. History of severe adverse reaction associated with a vaccine and/or severe allergic reaction (eg, anaphylaxis) to any component of the study intervention(s).	X
3. Immunocompromised individuals with known or suspected immunodeficiency, as determined by history and/or laboratory/physical examination.	X
4. Bleeding diathesis or condition associated with prolonged bleeding that would, in the opinion of the investigator, contraindicate intramuscular injection.	X
5. Women who are pregnant or breastfeeding.	X
6. Allergy to egg proteins (egg or egg products) or chicken proteins.	X
Prior/Concomitant Therapy:	
7. Any participant who has had significant exposure (someone who was within 6 feet of an infected person for a cumulative total of 15 minutes or more over a 24-hour period) to someone with laboratory-confirmed SARS-CoV-2 infection, COVID-19, or influenza in the past 14 days known prior to Visit 201.	X
8. Any participant who has a SARS-CoV-2 RT-PCR or antigen test in the past 10 days prior to Visit 201 that has not been confirmed as negative.	X
9. Individuals who receive treatment with radiotherapy or immunosuppressive therapy, including cytotoxic agents or systemic corticosteroids (if systemic corticosteroids are administered for ≥14 days at a dose of ≥20 mg/day of prednisone or equivalent), eg, for cancer or an autoimmune disease, or planned receipt throughout the study. Inhaled/nebulized, intra-articular, intrabursal, or topical (skin or eyes) corticosteroids are permitted.	X
10. Receipt of blood/plasma products, immunoglobulin, or monoclonal antibodies, from 60 days before study intervention administration, or planned receipt throughout the study.	X
11. Any participant who has received or plans to receive a modRNA-platform SARS-CoV-2 vaccine within 28 days of Visit 201.	X
12. Any participant who has received licensed influenza vaccination for the 2022-2023 northern hemisphere influenza season.	X
Prior/Concurrent Clinical Study Experience:	
13. Participation in other studies involving study intervention within 28 days prior to study entry and/or during study participation.	X

	Substudy B
Other Exclusions:	
14. Investigator site staff or Pfizer employees directly involved in the conduct of the study, site staff otherwise supervised by the investigator, and their respective family members.	X
15. Participation in strenuous or endurance exercise through Visit 205.	X
16. Prior history of heart disease.	X
17. Any abnormal screening troponin I laboratory value.	X
18. Screening 12-lead ECG that, as judged by the investigator, is consistent with probable or possible myocarditis or pericarditis, or demonstrates clinically relevant abnormalities that may affect participant safety or interpretation of study results. Participants with a screening 12-lead ECG that shows an average QTcF interval >450 msec, complete left bundle branch block, signs of an acute or indeterminate-age myocardial infarction, ST-T interval changes suggestive of myocardial ischemia, second- or third-degree AV block, or serious bradyarrhythmias or tachyarrhythmias should be excluded from study participation.	X

10.10.6. Substudy B Intervention and Concomitant Therapy

10.10.6.1. Study Intervention(s) Administered

Study interventions for Substudy B will include:

Intervention Name	mIRV	qIRV	QIV	Normal Saline Placebo
Type	Vaccine	Vaccine	Vaccine	Placebo
Dose Formulation	modRNA	modRNA		Normal saline (0.9% sodium chloride solution for injection)
Unit Dose Strength(s)	O.3 mL	O.3 mL	0.7 mL	
Dosage Level(s)	CCI	CCI		N/A
Route of Administration	Intramuscular injection	Intramuscular injection	Intramuscular injection	Intramuscular injection
Use	Experimental	Experimental	Experimental	Placebo for expanded enrollment
IMP or NIMP	IMP	IMP	IMP	IMP
Sourcing	Provided centrally by the sponsor			

Intervention Name	mIRV	qIRV	QIV	Normal Saline Placebo
Packaging and	Study intervention	Study intervention	Study intervention	Study intervention
Labeling	will be provided in a	will be provided in a	will be provided either	will be provided in a
	glass vial as open-	glass vial as open-	as a PFS or in a glass	glass or plastic vial as
	label supply. Each	label supply. Each	vial as open-label	open-label supply.
	vial will be labeled	vial will be labeled	supply. Each PFS/vial	Each vial will be
	as required per	as required per	will be labeled as	labeled as required
	country requirement	country requirement	required per country	per country
			requirement	requirement

mIRVs encoding HA for each A and B strain will be mixed at the site to generate either bIRV at a dose level of either CCI, or qIRV at dose level combinations other than CCI. Please see the IP manual for further details.

10.10.6.1.1. Administration

See Section 6.1.1.

During Substudy B, participants will receive study intervention as randomized at Visit 201 and, if applicable, at Visit 203 in accordance with the SoA (Section 10.10.1).

Study intervention should be administered intramuscularly as detailed in Table 6.

 Table 6.
 Substudy B Study Intervention Schedule

Participant	Vaccine	Study Intervention	- Vaccination 1	Study Intervention -	Vaccination 2
Age	Group	Right Deltoida	Left Deltoid	Right Deltoida	Left Deltoid
	1	qIRV CCI		qIRV CCI	
		2 x A, 2 x B		2 x A, 2 x B	
		CCI		CCI	
	2	Licensed QIV		bIRV CCI	
				2 x A CC	
	3	Licensed QIV		bIRV CC	
				2 x A CC	
	4	Licensed QIV		Licensed QIV	
	5	bIRV CC	Licensed QIV		
65.		2 x A CC			
65 to	6	bIRV CC	Licensed QIV		
85 years of		2 x A CC			
age		qIRV CCI			
	7	$2 \times A, 2 \times B$			
		CCI			
	8	Licensed QIV			
		bIRV CC	bIRV CC		
	9		2 x A		
		2 x B CC	CCI		
		qIRV CC			
	10	2 x A CC			
		2 x B CC			

PFIZER CONFIDENTIAL

Table 6. Substudy B Study Intervention Schedule

Participant	Vaccine	Study Intervention - Vaccination 1		ne Study Intervention - Vaccination 1 Study Intervention	Study Intervention -	Vaccination 2
Age	Group	Right Deltoid ^a	Left Deltoid	Right Deltoida	Left Deltoid	
	11	qIRV CCI 2 x A CCI 2 x B CCI				
	12	Licensed QIV			Placebo	
18 to	13	qIRV CCI 2 x A, 2 x B				
64 years of age	14	qIRV CCI 2 x A, 2 x B				

a. Local reactions will be assessed at the injection site on the right deltoid (see Section 8.2.3.2).

Study intervention in Substudy B will be administered in a single-blinded manner.

10.10.6.1.2. Medical Devices

See Section 6.1.2.

10.10.6.1.3. Preparation, Handling, Storage, and Accountability

See Section 6.2.

10.10.6.1.4. Preparation and Dispensing

See Section 6.2.1.

During Substudy B, study intervention will be prepared by qualified site personnel according to the IP manual or package insert and the study intervention administered in such a way to ensure that the participants remain blinded.

10.10.6.2. Measures to Minimize Bias: Randomization and Blinding

10.10.6.2.1. Allocation to Study Intervention

See Section 6.3.1.

Allocation of study intervention at Visit 201 in Substudy B will be conducted via IRT.

10.10.6.2.2. Blinding of Site Personnel

Substudy B is single-blinded, such that all site personnel, including the investigator, investigator staff, and study staff receiving, storing, dispensing, preparing, and administering the study interventions will be unblinded. Study participants, however, will remain blinded to which 1- or 2-visit vaccination schedule they receive (see Section 10.10.4.1).

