8.2.3.2. Local Reactions

During the reactogenicity e-diary reporting period, participants will be asked to assess redness, swelling, and pain at the injection site and to record the symptoms in the reactogenicity e-diary. In Substudy B, local reactions will be assessed at the injection site on the right arm only.

If a local reaction persists beyond the end of the reactogenicity e-diary period following vaccination, the participant will be requested to report that information. The investigator will enter this additional information in the CRF.

Participants will be provided with a measuring device. Redness and swelling will be measured and recorded in measuring device units (range: 1 to 21) and then categorized during analysis as absent, mild, moderate, or severe based on the grading scale in Table 1. Measuring device units can be converted to centimeters according to the following formula: 1 measuring device unit = 0.5 cm. Pain at the injection site will be assessed by the participant as absent, mild, moderate, or severe according to the grading scale in Table 1.

If a Grade 3 local reaction is reported in the reactogenicity e-diary, a telephone contact should occur to ascertain further details and determine whether a site visit is clinically indicated. Only an investigator or medically qualified person is able to classify a participant's local reaction as Grade 4. If a participant experiences a confirmed Grade 4 local reaction, the investigator must immediately notify the sponsor and, if it is determined to be related to the administration of the study intervention, further vaccinations will be discontinued in that participant.

Table 1. Local Reaction Grading Scale

	Mild (Grade 1)	Moderate (Grade 2)	Severe (Grade 3)	Potentially Life-Threatening (Grade 4)
Pain at the injection site	Does not interfere with activity	Interferes with activity	Prevents daily activity	Emergency room visit or hospitalization for severe pain
Redness	>2.0 cm to 5.0 cm (5 to 10 measuring device units)	>5.0 cm to 10.0 cm (11 to 20 measuring device units)	>10 cm (≥21 measuring device units)	Necrosis or exfoliative dermatitis

Table 1. Local Reaction Grading Scale

	Mild (Grade 1)	Moderate (Grade 2)	Severe (Grade 3)	Potentially Life-Threatening (Grade 4)
Swelling	>2.0 cm to 5.0 cm	>5.0 cm to 10.0 cm	>10 cm	Necrosis
	(5 to 10 measuring	(11 to 20 measuring	(≥21 measuring	
	device units)	device units)	device units)	

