8.2.3.3. Systemic Events

During the reactogenicity e-diary reporting period, participants will be asked to assess vomiting, diarrhea, headache, fatigue, chills, new or worsened muscle pain, and new or worsened joint pain and to record the symptoms in the reactogenicity e-diary. The symptoms will be assessed by the participant as absent, mild, moderate, or severe according to the grading scale in Table 2.

If a Grade 3 systemic event is reported in the reactogenicity e-diary, a telephone contact should occur to ascertain further details and determine whether a site visit is clinically indicated. Only an investigator or medically qualified person is able to classify a participant's systemic event as Grade 4. If a participant experiences a confirmed Grade 4 systemic event, the investigator must immediately notify the sponsor and, if it is determined to be related to the administration of the study intervention, further vaccinations will be discontinued in that participant.

Table 2. Systemic Event Grading Scale

	Mild (Grade 1)	Moderate (Grade 2)	Severe (Grade 3)	Potentially Life- Threatening (Grade 4)	
Vomiting	1-2 times in 24 hours	>2 times in 24 hours	Requires IV hydration	Emergency room visit or hospitalization for hypotensive shock	
Diarrhea	2 to 3 loose stools in 24 hours	4 to 5 loose stools in 24 hours	6 or more loose stools in 24 hours	Emergency room visit or hospitalization for severe diarrhea	
Headache	Does not interfere with activity	Some interference with activity	Prevents daily routine activity	Emergency room visit or hospitalization for severe headache	
Fatigue/tiredness	Does not interfere with activity	Some interference with activity	Prevents daily routine activity	Emergency room visit or hospitalization for severe fatigue	
Chills	Does not interfere with activity	Some interference with activity	Prevents daily routine activity	Emergency room visit or hospitalization for severe chills	
New or worsened muscle pain	Does not interfere with activity	Some interference with activity	Prevents daily routine activity	Emergency room visit or hospitalization for severe new or worsened muscle pain	

PFIZER CONFIDENTIAL

Table 2. Systemic Event Grading Scale

	Mild (Grade 1)	Moderate (Grade 2)	Severe (Grade 3)	Potentially Life- Threatening (Grade 4)
New or worsened joint pain	Does not interfere with activity	Some interference with activity	Prevents daily routine activity	Emergency room visit or hospitalization for severe new or worsened joint pain

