Explain to the participant e-diary completion requirements and assist the participant with downloading the app or issue provisioned device if required		X							
Provide thermometer and measuring device		X							
Review reactogenicity e-diary data (daily review is optimal during the active diary period)		-		•			•		
Review ongoing reactogenicity e-diary symptoms and obtain stop dates			X	X		X	X		

Visit Number	Screening	201	202	203	204	205	206	207	208
Visit Description	Screening	Vaccination	1-Week	Vaccination	Day 3	1-Week	4-Week	8-Week	6-Month
Visit Description		1	Post-	2 ^b	Follow-	Follow-	Follow-	Follow-	Telephone
			Vaccination 1		up Visit	up Visit	up Visit	up Visit	Contact
			Visita						
Visit Window (Days)	0 to 28 Days	Day 1	6 to 8	19 to 23	2 to 4	6 to 8	26 to 30	52 to 60	175 to 189
	Before		Days	Days After	Days	Days	Days	Days	Days
	Visit 201			Visit 201					
					the nu	mber of d	days indic		cted within tive to the ation
Collect AEs and SAEs as appropriate	X	X	X	X	X	X	Xe	Xe	X
Collect e-diary or assist the participant with deleting application						Xf	X		

Abbreviations: COVID-19 = coronavirus disease 2019; ECG = electrocardiography.

- a. Visit 202 is to be conducted during initial enrollment for participants assigned to a 2-visit vaccination schedule only.
- b. Vaccination 2 (Visit 203) is only conducted for participants randomized to receive a 2-visit vaccination schedule.
- c. Physical examination at Visit 201 will be conducted if clinically indicated.
- d. Additional 50 mL for cell-mediated immunogenicity assessments as detailed in Section 10.10.4.
- e. Any AEs occurring up to 48 hours after the blood draw must be recorded (see Section 8.3).
- f. If Visit 205 is conducted after Day 7.

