5.2.1.1. Safety Data

All safety analyses will be performed on the safety populations.

For safety data, as defined in Section 3.1.1, the exact 2-sided 95% CIs using the Clopper and Pearson method will be provided by vaccine group for all primary safety endpoints and for proportions of participants reporting local reactions, systemic events, AEs (including immediate AEs), SAEs, abnormal troponin I values, and new ECG abnormalities. The 95% CI for the between-group difference for binary endpoints will be calculated using the Miettinen and Nurminen method.

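### Substudy B participants are blinded only among groups with the same visible injection pattern, not to their 1- or 2-visit schedule as the plan states

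*Protocol*

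**What the plan says.** Substudy B is described as single-blinded. Protocol 10.10.6.2.2 unblinds all site personnel, and 10.10.6.2.3 unblinds the sponsor. The participant is the only blinded party: "Study participants, however, will remain blinded to which 1- or 2-visit vaccination schedule they receive". Protocol 10.10.4.1 says that participants aged 65 to 85 "will be blinded to which 1-visit or 2-visit vaccination schedules they will receive", and SAP 2.3.1 repeats this. On method, Protocol 10.10.6.1.4 says only that products are prepared and "the study intervention administered in such a way to ensure that the participants remain blinded".

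Table 6 (Protocol 10.10.6.1.1) fixes the arm and visit of every injection. Placebo appears once, in the left deltoid at Vaccination 2 of Group 12. Footnote b of the Substudy B schedule of activities says: "Vaccination 2 (Visit 203) is only conducted for participants randomized to receive a 2-visit vaccination schedule". Footnote a limits Visit 202 to 2-visit participants in initial enrollment. Visit 204 falls 2 to 4 days after the last vaccination.

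Solicited events are primary safety endpoints recorded in a 7-day e-diary. On local reactions: "Pain at the injection site will be assessed by the participant as absent, mild, moderate, or severe" (Protocol 8.2.3.2). On systemic events: "The symptoms will be assessed by the participant as absent, mild, moderate, or severe according to the grading scale in Table 2" (Protocol 8.2.3.3). For binary safety data, SAP 5.2.1.1 adds: "The 95% CI for the between-group difference for binary endpoints will be calculated using the Miettinen and Nurminen method". It names no pairs of groups.

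**The concern.** A participant can see how many injections were given, in which arm, and when the next visit is. If these differ by group, the stated blinding cannot hold across groups. It is also the only masking in Substudy B. In Substudy A, by contrast, the staff who evaluate safety are blinded (Protocol 10.9.6.2.2).

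At stake is how between-group differences in self-rated pain, fatigue, headache, chills, muscle pain and joint pain are read. A participant who knows that modRNA was given may report more symptoms through expectation. A report that calls every contrast single-blind would give the reader no warning of this. The absence of hypothesis tests does not remove such a bias from a descriptive difference.

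**Working it through.** **Inputs.** Arms and visits of injection come from Table 6 of the protocol. Visit structure comes from the Substudy B schedule of activities and Protocol 10.10.8.8.3 to 10.10.8.8.5. Group count and size come from Protocol 9.5.

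**Plan's own figure.** 11 groups × 15 = 165 in initial enrollment, as stated in Protocol 1.1 and SAP 2.3.1. Protocol 10.10.4.1 gives about 90, which 11 × 15 does not reproduce. I use 165.

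**Step 1: sort the 11 initial-enrollment groups by what a participant can see.**

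| Visible pattern | Groups | Groups containing modRNA |
|---|---|---|
| Right arm, at two visits | 1, 2, 3, 4 | 3 of 4 |
| Both arms, at one visit | 5, 6, 9 | 3 of 3 |
| Right arm, at one visit | 7, 8, 10, 11 | 3 of 4 |

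In expanded enrollment, Group 12 receives QIV in the right arm and then placebo in the left. It matches Groups 1-4 through the first injection and its diary, and departs from them at the second. Groups 13 and 14 (18 to 64 years) each receive one right-arm injection, and both are qIRV.

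**Step 2: when the schedule type shows.** A 1-visit participant returns for Visit 204 at 2 to 4 days after Visit 201. A 2-visit participant does not; in initial enrollment the next visit is Visit 202, at 6 to 8 days. The difference appears inside the first 7-day diary period and is settled by Visit 203.

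**Step 3: who can infer modRNA.** Every two-arm group contains modRNA, and no QIV-only group receives two injections at one visit. Groups 5, 6 and 9 can therefore infer modRNA receipt on Day 1: 3 × 15 = 45, and 45/165 = 27.3%. Groups 13 and 14 can infer it because their age range has no other product. Groups 1-4 and Groups 7, 8, 10 and 11 each include a QIV-only control (Groups 4 and 8), so their participants cannot infer it from the pattern.

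**Step 4: group pairs that share a pattern, initial enrollment.**

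- All pairs: 11 × 10 / 2 = 55.
- Same-pattern pairs: 4 × 3 / 2 = 6, plus 3 × 2 / 2 = 3, plus 4 × 3 / 2 = 6, total 15.
- Share: 15/55 = 27.3%. The other 40 pairs cross patterns.

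Group 12 is left out of this count because it exists only in expanded enrollment and SAP 5.2 analyses the two stages separately. No pair count is possible for expanded enrollment, since the sponsor's internal review committee chooses its groups later.

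**The case against.** **The blinding sentence can be read more narrowly**, as blinding to which schedule within the 1-visit or the 2-visit class. SAP 2.3.1 speaks of adults aged 18 to 64 in that sense. On that reading the visit count breaks nothing. The reading is fair but does not rescue the statement. Groups 5, 6 and 9 and Groups 7, 8, 10 and 11 are all 1-visit and differ in number of injections; Group 12 differs from Groups 1-4 within the 2-visit class.

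**A reader might infer that Groups 5, 6 or 9 against Group 8 is in effect open-label.** The documents do not support that. Group 8 shares its pattern with three modRNA groups, so its participants cannot tell that they received QIV. Participants in Groups 5, 6 and 9 cannot tell which of the three they are in. The unmasking is partial and on one side.

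**Not every solicited endpoint is a subjective self-rating.** This stands. Redness and swelling are measured with a device, temperature with a thermometer, and Grade 4 is assigned by an investigator or medically qualified person. The exposure lies mainly in pain and systemic symptoms below Grade 4.

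**No reactogenicity contrast is actually listed.** SAP 6.1.1.1 and 6.1.1.2 report per-group proportions with Clopper-Pearson intervals. SAP 5.2.1.1 names a method for differences but no pairs. This stands and limits the weight of the point, but the provision is open to any pair and nothing warns the reader.

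**Removing cross-pattern intervals would lose useful information.** This also stands. Protocol 2.3.1 lists concurrent bIRV and QIV as having an unknown safety profile, so those estimates are wanted.

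**Conclusion.** The point holds in a limited form. The stated participant blinding is broader than the design provides: it holds only within same-pattern sets, which is 15 of 55 pairs (27%) in initial enrollment. In that stage, 45 of 165 participants (27%) can infer modRNA receipt on Day 1, as can Groups 13 and 14 in expanded enrollment.

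It would go too far to say that the pattern reveals each participant's exact group or, in general, modRNA against QIV. Each one-arm pattern in initial enrollment still holds four groups, one of them QIV-only. HAI, troponin I and ECG results do not rest on self-rating and are not the concern.

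Assumptions:

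- Participants know the list of schedules. The consent form is not available, so recognition of modRNA is an inference; the injections and visits themselves are seen regardless.
- The IP manual, also not available, adds no sham procedure.
- All groups sharing a pattern are open together. Protocol 10.10.4.1 allows as few as two groups open at a time, which could weaken blinding within a pattern.

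The documents give no basis for sizing any bias. Upward reporting among those who infer modRNA is plausible but not shown.

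**What to change.** 1. In Protocol 10.10.4.1 and 10.10.6.2.2 and SAP 2.3.1, state that participants are blinded only among groups with the same number, arm and visits of injection. List the sets: Groups 1-4; 5, 6 and 9; 7, 8, 10 and 11; 13 and 14. Add that Group 12 matches Groups 1-4 only until its second injection.
2. In SAP 5.2.1.1, keep the between-group difference intervals. State that any e-diary difference between groups with different visible patterns, including Group 12 against 1-visit groups, is not participant-blinded and will be reported and interpreted as such.
3. Name the same-pattern contrasts as the participant-blinded ones: Groups 7, 10 and 11 against 8; Groups 1, 2 and 3 against 4; Group 13 against 14.

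The cost is wording in two documents and a footnote on affected tables. No dose, visit or procedure changes, and no estimate is dropped. The drawback is that the plan must acknowledge that Groups 5, 6 and 9 have no fully blinded QIV comparator for solicited events.
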